#### Exclusion Criteria:

- under 18 years of age
- Unable to provide consent (no use of LAR)
- History of dementia or Alzheimer's disease
- Patient residing in a residential care facility prior to admission (i.e, skilled nursing facility, nursing home, assisted living facility)

#### Treatment Groups:

The prospectively enrolled patients will have TENS pads placed immediately following surgery, prior to PACU. The TENS unit will be connected to the pads and turned on in the PACU. Each patient will receive instructions for suggested use of the device. They will be allowed to individualize the frequency/amplitude of the current to reach a "strong sub-noxious" stimulation, as recommended by previous studies. They will be asked to aim for 4x45 minute sessions each day. This protocol was previously published by a separate group demonstrating decreased post-operative pain levels with adjunctive TENS use.

This institution has an ongoing research study which collects injury characteristics, patient-reported outcomes, and kinematic/performance data for orthopaedic trauma patients with lower-extremity injuries. Patients with similar injuries as the prospectively enrolled patients will be identified in this database to serve as controls, because TENS units were not previously used at this institution for pain management. Our institution also has a database of all opioid prescriptions as well as risk factors that can be used to provide these data for the controls.

#### Sample Size:

The sample size estimate was based on data from the meta-analysis conducted by Tedesco et al. This is a superiority prospective observational study with matched historical controls and the primary outcome variable is morphine milligram equivalents (MME) within the first 48 hours postoperatively. The assumed mean MME for the TENS group is 6.4 and 9.9 for the control group with a pooled standard deviation of 5.5. Using a two-sided independent T-test, .05 level of significance and 80% power, 40 patients per group is needed for a total study sample of 80 patients. Therefore, we will enroll 50 patients in order to account for loss to follow-up. Historical controls will be injury-matched from a prospectively collected, historical database on mobility (N=50).

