## Transcutaneous Electrical Nerve Stimulation (TENS) for Pain Alleviation in Perioperative Fracture Patients

### Specific Aims:

Opioid overdoses continue to increase, and the path to addiction often begins with a prescription. Half of postoperative patients receive an opioid prescription. Multimodal pain management, including cognitive, physical, and pharmaceutical strategies, reduces reliance on opioids alone. Transcutaneous nerve stimulation (TENS) is one physical strategy; this study aims to evaluate the effectiveness of TENS as part of postoperative pain management.

**Specific Aim 1:** To pilot the use of TENS among a postoperative lower extremity injury population as part of multimodal pain management.

$H_0$ : TENS cannot be delivered safely among this population.

$H_A$ : TENS can be delivered safely among this population.

**Specific Aim 2:** To compare utilization of inpatient and outpatient pain medications of patients treated with TENS and historical controls.

$H_0$ : Patients treated with TENS will require the same amount of opioids as historical controls.

$H_A$ : Patients treated with TENS will require less opioids (lower morphine milligram equivalent – MME) than historical controls during hospitalization and throughout 3-month follow up.

**Specific Aim 3:** To compare patient-reported outcomes of patients treated with TENS and historical controls.

$H_0$  1: Patients treated with TENS will experience equivalent patient-reported outcomes as compared to historical controls.

$H_A$  1: Patients treated with TENS will experience greater improvement in patient-reported outcomes (PROMIS 29) relative to baseline as compared to historical controls.

$H_0$  2: Patients treated with TENS will report higher pain scores as compared to historical controls.

$H_A$  2: Patients treated with TENS will report equivalent or lower pain scores as compared to historical controls.

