#### Outcome Measures:

**Primary Outcomes:** The primary outcome will be inpatient and outpatient opioid use, defined as morphine milligram equivalents. Morphine milligram equivalent dose (MME) will be calculated to standardize across different medications. Pill counts will be conducted at follow-up visits to account for unused opioids, and patients will be provided with opioid disposal kits. Use of non-opioid pain medications (i.e. NSAIDS, acetaminophen, gabapentin) will be documented. Patients will also be asked about their use of nonpharmaceutical modalities at each follow-up visit or phone call, including cryotherapy, aromatherapy, and cognitive strategies.

**Secondary Outcomes:** The secondary outcomes will be patient-reported outcomes, measured by the PROMIS 29, which includes physical function, anxiety, depression, fatigue, sleep disturbance, ability to participate in social roles and activities, pain interference and pain intensity. In addition, pain scores from the inpatient stay and clinic visits will be abstracted from the medical record. PROMIS will be administered during the hospitalization and at follow-up visits or via phone calls, emails, or text messages at 2, 6, and 12 weeks. VAS pain scores will be abstracted from the medical record during the hospitalization and at each follow-up visit.

**Process Measures and Feasibility:** Process measures will be collected to document feasibility of implementing TENS postoperatively among this patient population, including: patient compliance with TENS after discharge, number of times each day TENS was used, duration of each TENS session, and average frequency/amplitude of electrical current for each patient.

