#### Study Procedures:

**Screening & Enrollment:** All patients 18 years or older presenting for initial treatment, nonunion or limb length deformity correction of the femur, tibia (plateau, shaft, pilon), or hindfoot/ankle will be screened for eligibility. Once eligibility has been confirmed, a research coordinator and/or investigator will approach patient for consent prior to surgery. Patients will be given the opportunity to review the informed consent document and ask questions about the study. The informed consent will comply with the ICH/GCP regulatory guidelines.

**Baseline:** Once consent is obtained, baseline data regarding participant characteristics, injury characteristics and PROMIS scores will be collected from the participant and entered into the electronic data collection system. Data will also be collected from the medical record regarding injury characteristics, fracture fixation, pain scores and utilization of pain alleviation modalities (pharmaceutical and nonpharmaceutical).

**Follow-up:** Participants will complete study visits at 2, 6, and 12 weeks following admission to the hospital, which may overlap with regularly scheduled standard of care clinic visits. These visits may also be completed via phone calls, text messages, or email. At these visits, participants will be asked to complete PROMIS-29 survey. Data regarding use of any pharmaceutical and nonpharmaceutical modalities for pain management will be collected at these visits. Additional variables about fracture complications will be collected from the electronic medical record.

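### The protocol names two different primary outcomes, 48-hour MME and inpatient-plus-outpatient opioid use, and sizes the study on only the first

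*Protocol*

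**What the plan says.** Three sections of the protocol bear on which opioid outcome decides the study.

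- **Sample Size** describes a superiority comparison and states that "the primary outcome variable is morphine milligram equivalents (MME) within the first 48 hours postoperatively". Its planning values belong to that outcome: "The assumed mean MME for the TENS group is 6.4 and 9.9 for the control group", with a pooled SD of 5.5, a two-sided independent t-test at 0.05 and 80% power. This gives 40 per group. Enrolment is then raised: "Therefore, we will enroll 50 patients in order to account for loss to follow-up". Fifty historical controls are to be matched.
- **Outcome Measures**, under Primary Outcomes, states: "The primary outcome will be inpatient and outpatient opioid use, defined as morphine milligram equivalents". It gives no time window and adds: "Pill counts will be conducted at follow-up visits to account for unused opioids". Study Procedures sets the timing of those visits: "Participants will complete study visits at 2, 6, and 12 weeks following admission to the hospital".
- **Specific Aims**, Aim 2, puts the opioid hypothesis over a third period: lower MME "than historical controls during hospitalization and throughout 3-month follow up".

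**The concern.** Sample Size and Outcome Measures each call something the primary outcome, and the two are not the same quantity. A total over the first 48 hours after surgery cannot contain outpatient use counted at visits up to 12 weeks. Outcome Measures also leaves open whether inpatient and outpatient use form one sum or two outcomes: the paragraph label is plural and the sentence is singular.

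Two things are at stake. First, the 80% power applies to 48-hour MME only. If Outcome Measures governs, the power of the primary comparison is neither stated nor derivable. Second, the results may diverge. The device is used in hospital and then at home, so 48-hour MME could be lower with TENS while outpatient MME shows no difference, or the reverse. Either reading could then cite the protocol, and the deciding outcome could be chosen after the data are known. The study is not randomised and draws its controls from existing databases, so naming that outcome in advance is an important safeguard.

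**Working it through.** **1. Reproduce the stated sample size (48-hour MME).** Inputs from Sample Size: means 6.4 and 9.9, SD 5.5, two-sided alpha 0.05, power 80%.

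- Difference = 9.9 − 6.4 = 3.5 MME. Standardised difference d = 3.5 / 5.5 = 0.636.
- Normal approximation: n = 2 × (1.960 + 0.842)² / 0.636² = 38.8, so 39 per group.
- Exact calculation for the t-test (noncentral t): n = 39.75, so 40 per group. This matches the protocol.
- Power is 80.3% with 40 against 40. It is 84.3% with 40 TENS patients and all 50 controls.

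The arithmetic in Sample Size is therefore right for the outcome it names.

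**2. Try the same for the Outcome Measures definition.** The calculation needs a difference and an SD. The protocol's only MME means and SD are those above, attached to the 48-hour outcome. No sample size or power can be computed. What can be computed is the effect that the planned numbers would detect for any outcome analysed with the same test at 80% power:

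| Analysable patients | Detectable difference |
|---|---|
| 40 TENS, 40 controls | 0.634 SD |
| 40 TENS, 50 controls | 0.601 SD |

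Whether the broader outcome has an effect that large cannot be judged from the protocol.

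**3. Compare what each definition covers.**

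| | Sample Size | Outcome Measures |
|---|---|---|
| Quantity | MME | MME, inpatient and outpatient |
| Window | First 48 hours after surgery | None stated; Aim 2 suggests hospitalisation to 3 months |
| Outpatient measurement | None mentioned | Pill counts at follow-up visits (2, 6, 12 weeks) |
| Planning mean and SD | Given | None |

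**4. Illustration: what an either-or claim would do to the error rate.** The protocol does not say that success may be claimed on either definition. Suppose it were, with each outcome tested at two-sided 0.05 and the broader outcome taken as a single one. Each test has a 2.5% chance of a false claim in the direction of benefit. With independent outcomes, the chance of at least one is 1 − 0.975² = 4.94%. For correlated outcomes (bivariate normal, no true effect, assumed correlations):

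| Correlation | Chance of a false claim of benefit |
|---|---|
| 0 | 4.94% |
| 0.5 | 4.54% |
| 0.7 | 4.17% |
| 0.9 | 3.52% |

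The figure for one outcome is 2.5%. The finding does not depend on these rates.

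**The case against.** The best defence is a nested reading. Outcome Measures names the domain, opioid use in MME, without a window. Sample Size then names the operational variable, with the only explicit window, test and alpha. Aim 2 is simply the wider hypothesis. A patient discharged early might even have some outpatient use inside the 48 hours. But the protocol never states this nesting, and pill counts at follow-up visits reach far beyond 48 hours. The reading softens the conflict without removing it.

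A second objection is that summing rules and alpha handling usually belong in a SAP, which may exist and is not shown. That is fair for those details, and they are not the ground of this finding. The conflict over which outcome is primary is in the protocol's own text, and a SAP would leave that text inconsistent.

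A third is that this is a single-centre observational study with a pilot aim, that its sample size is correct for the outcome it names, and that no power shortfall is shown. All of that is true. However, only Aim 1 is described as a pilot. Sample Size declares a superiority comparison with 80% power at 0.05, and that claim needs one defined primary outcome.

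**Conclusion.** The concern holds and must be fixed. Two current sections of the protocol label different quantities as primary, and nothing reconciles them. The stated 40 per group and 80% power are correct for 48-hour MME and say nothing about inpatient-plus-outpatient MME. For the latter, power is unknown: it reaches 80% only if the true difference is at least about 0.63 SD with 40 analysable per group, or 0.60 SD with 40 TENS patients and 50 controls, assuming the same t-test. The severity rests on the contradiction in the outcome that decides the study, and not on any demonstrated loss of power or inflation of error.

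**What to change.** State one primary outcome, with its time window, in identical words in Sample Size and Outcome Measures. Which window is primary is the sponsor's decision.

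**Option A: keep 48-hour MME.** Rewrite the Primary Outcomes paragraph to name MME over the first 48 hours after surgery as the sole primary outcome. List inpatient-stay MME and outpatient MME through 12 weeks as secondary outcomes. These still address the period in Aim 2; a short clause there saying which outcome is primary would help. This is a wording change with no extra patients, and the sample size stands. The drawback is that outpatient use is no longer primary although the units go home with patients.

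**Option B: use the longer window.** State whether inpatient and outpatient use are summed or are separate outcomes, and give the end time, planning mean, SD and alpha. Then restate the power at the number expected to be analysable. Under the protocol's own allowance that is 40 in the TENS group, not 50.

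Option B may need more patients and controls. As illustration only, with assumed effects that the protocol does not give, 0.5 SD needs 64 analysable per group and 0.4 SD needs 100. The loss implied by 40 of 50 is 1 − 40/50 = 20%, a rate the protocol does not state. At that rate, TENS enrolment would be 64 / 0.8 = 80 or 100 / 0.8 = 125.

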### Background and Significance:

Transcutaneous electrical nerve stimulation (TENS) is an affordable and non-invasive option for post-operative analgesia. Broadly, TENS devices deliver pulsed electrical impulses across skin to modulate pain. They are theorized to work through different mechanisms at multiple physiologic levels. Centrally, TENS units activate small-diameter sensory afferents (A $\delta$  nerve fibers), which in turn activate descending pain-inhibitory networks. Peripherally, TENS activation of both large- and small-diameter sensory afferents blocks nociceptive signals to the

brain and is instead perceived as TENS-induced paresthesias. Finally, TENS efficacy may also be mediated by  $\mu$ -opioid, 5HT-1, and 5HT-2 receptors, particularly at low-frequency electrical activity.

There are inconclusive results for the adjunctive use of TENS to modulate pain, largely because of a relative paucity of high-quality trials and significant inter-study heterogeneity due to non-standardized protocols. Moreover, most studies within the orthopaedic literature have been concentrated primarily within the total knee arthroplasty (TKA) literature and may have limited generalizability to orthopaedic trauma patients. Some studies have shown a trend towards decreased opioid consumption with the adjunctive use of TENS (vs. placebo-TENS or standard care) while other studies have shown no difference in pain scores in the post-operative period. To our knowledge, only two recent RCTs have been conducted on non-TKA orthopaedic populations, both of which show promise for the use of TENS postoperatively. One prospective double-blind randomized trial on arthroscopic rotator cuff repairs found a 25% reduction in post-operative opioid consumption when TENS was used adjunctively for pain control. Another single-blind prospective RCT on Colles' fractures reported greater postoperative pain improvements in patients receiving TENS vs. placebo.

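### Does taking the planning means and SD from knee-replacement trials leave this trauma study underpowered?

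*Protocol*

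**What the plan says.** The Sample Size section of the Protocol names the powered endpoint: "the primary outcome variable is morphine milligram equivalents (MME) within the first 48 hours postoperatively". Its planning values are these: "The assumed mean MME for the TENS group is 6.4 and 9.9 for the control group with a pooled standard deviation of 5.5". The result is given as: "Using a two-sided independent T-test, .05 level of significance and 80% power, 40 patients per group is needed for a total study sample of 80". The section then adds a margin: "Therefore, we will enroll 50 patients in order to account for loss to follow-up". It also sets the number of matched historical controls at 50.

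The planning values are credited to a meta-analysis. The superscript there points to item 2 of the reference list, a general article on TENS. The meta-analysis named in the sentence is item 3, whose title limits it to total knee arthroplasty. The mismatched superscript is a clerical slip.

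The Background says that most orthopaedic TENS studies are in knee arthroplasty and that this literature "may have limited generalizability to orthopaedic trauma patients". It describes two trials outside knee arthroplasty. One, in arthroscopic rotator cuff repair, "found a 25% reduction in post-operative opioid consumption when TENS was used adjunctively for pain control". The other, in wrist fracture, is described by pain scores only.

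Under Treatment Groups, controls come from an existing institutional database, "because TENS units were not previously used at this institution for pain management". The same section says that a second database, of opioid prescriptions, can supply opioid data for them.

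**The concern.** The protocol doubts that knee-replacement evidence carries over to trauma, then takes its control mean, effect and SD from that evidence without giving a reason or a range. The cohort covers the femur, tibia, hindfoot and ankle, and mixes fresh fractures, nonunion and deformity correction. Nothing suggests that opioid use would have the spread seen after one elective operation. The assumed effect is also larger than the only opioid reduction the Background quantifies.

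Because the controls have already been treated, their 48-hour opioid use looks like something that could be extracted before enrolment instead of borrowed. If the true effect is smaller or the true SD larger than assumed, power falls below 80%, and a null result could be misread as evidence that TENS does not reduce opioid use.

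**Working it through.** **Inputs (Protocol, Sample Size):** means 6.4 and 9.9 MME, SD 5.5, two-sided alpha 0.05, power 80%, independent t-test, 40 per group analysed, 50 TENS patients enrolled and 50 controls. From the Background: a 25% reduction in the rotator cuff trial.

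**1. The plan's own figure.**
- Difference = 9.9 − 6.4 = 3.5 MME, a reduction of 3.5/9.9 = 35.4%.
- Standardised difference d = 3.5/5.5 = 0.636.
- Normal approximation: n = 2 × (1.960 + 0.842)² / d² = 38.8, so 39 per group.
- Exact noncentral t-test: 39.75, so 40 per group, as stated.
- Power by the t-test: 80.3% at 40 per group, 84.3% with 40 TENS patients and 50 controls, 88.3% at 50 per group.
- Difference detectable with 80% power at SD 5.5: 3.49 MME at 40 per group, 3.11 MME at 50.

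**2. A 25% reduction with the same control mean and SD.**
- Difference = 0.25 × 9.9 = 2.475 MME; d = 2.475/5.5 = 0.45.
- Power: 51.1% at 40 per group, 55.5% at 40 versus 50, 60.6% at 50 per group.
- For 80% power: 78.5, so 79 per group.

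**3. The 3.5 MME difference kept and the SD varied.** Every SD other than 5.5 is an assumption; the protocol gives none.

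| SD | Power, 40 per group | Power, 50 per group |
|---|---|---|
| 4.5 | 93% | 97% |
| 5 | 87% | 93% |
| 5.5 (protocol) | 80% | 88% |
| 6 | 73% | 82% |
| 7 | 60% | 70% |
| 8 | 49% | 58% |
| 11 | 29% | 35% |

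**4. Mean and SD moving together.** For a fixed percentage reduction r, d = r × mean / SD, so power depends only on r and the ratio SD/mean (5.5/9.9 = 0.556 in the plan). If trauma patients used twice as much opioid with twice the spread, a 35.4% reduction would be 7 MME against an SD of 11. Then d = 7/11 = 0.636 and power at 40 per group is again 80.3%. The 29% in the last row of the table arises because the SD is doubled while the difference in MME is held still.

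**The case for a change.** The strongest case for acting is that the protocol undercuts its own planning source and offers nothing in its place. At 40 per group the detectable difference, 3.49 MME, almost equals the assumed 3.5, so the only slack lies in the extra 10 patients. The comparison cannot be made at all unless the controls' 48-hour opioid use can be retrieved, so extracting it early would be useful whatever it showed. The cost is one query and one rewritten paragraph.

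Part of this stands. The source is knee arthroplasty, the Background does express doubt, and no range is shown. The rest is weaker than it looks:

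- **The 25% is no better as a benchmark.** It comes from arthroscopic shoulder surgery, which is neither lower extremity nor fracture, and the protocol gives no time window for it. If knee data are too remote, so are these.
- **The 51% to 61% needs the disputed figures.** It depends on an SD/mean ratio of 0.556, which comes from the knee meta-analysis.
- **The direction of any error is unknown.** A smaller SD raises power, and so does a higher control mean with the same SD and percentage reduction.
- **Early availability is an inference.** The protocol describes a mobility database and a prescription database. It does not say that either holds opioids given in hospital within 48 hours. The planned comparison will need those data in the end, but the protocol does not show that they can be had before enrolment.
- **The query has a cost of its own.** Controls are matched to the patients enrolled, so only a wider pool could be queried beforehand. Looking at control outcomes before matching is settled would also open the way to choosing controls with outcomes in view.

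**Conclusion.** No change is called for. The sample size is correct on its stated inputs (40 per group, 80.3% power), and planning for 50 per group raises power to 88.3% on those inputs. A 48-hour outcome measured soon after surgery should lose few patients, so the 40-per-group figures are probably the pessimistic end; that is a judgement, since the protocol gives no loss rate at 48 hours.

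The lower powers, 51% to 61% for a 25% reduction and 29% to 58% for SDs of 8 to 11 with the difference held at 3.5 MME, are valid sensitivity figures under assumptions that the protocol neither makes nor contradicts. They do not show that the trial misses a figure it states. Borrowing from a meta-analysis is ordinary when, as the Background says, good trials are few.

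Rewriting the power paragraph would leave the enrolment number, the comparison and the results as they are. The analysis will use the SD observed in this cohort, and the confidence interval for the difference will show how much a null result can rule out. What remains is a low-severity planning note: the inputs are carried over from knee arthroplasty without a stated reason or a sensitivity range.

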## **Research Design and Method:**

### Overall Design

This will be a prospective observational study of patients undergoing operative treatment of lower extremity conditions, including fracture fixation, treatment of nonunion, and deformity correction. The study will be conducted at a single Level I trauma center. Enrolled patients will receive TENS postoperatively during hospitalization; TENS units will also be sent home with patients for use throughout recovery. This group will be compared to controls injury-matched from a prospectively collected, historical database on mobility who did not receive treatment with TENS.

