### Inclusion Criteria:

- Operative treatment of lower extremity conditions, including fracture fixation, treatment of nonunion, and deformity correction
- Injury or deformity of the femur, tibia (plateau, shaft, pilon), or hindfoot and ankle
- Isolated injury
- 18 years or older
- Able to provide consent

- Plan for discharge to home

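### Should the protocol take more than 50 historical controls, given that they come from an existing database?

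*Protocol*

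**What the plan says.** The Sample Size section names MME in the first 48 hours after surgery as the primary variable and gives the planning values: "The assumed mean MME for the TENS group is 6.4 and 9.9 for the control group with a pooled standard deviation of 5.5". With a two-sided independent t-test at the 0.05 level and 80% power it arrives at 40 per group, 80 in total. It continues: "Therefore, we will enroll 50 patients in order to account for loss to follow-up". The control group follows directly: "Historical controls will be injury-matched from a prospectively collected, historical database on mobility (N=50").

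Overall Design describes the same source: "This group will be compared to controls injury-matched from a prospectively collected, historical database on mobility who did not receive treatment with TENS". Treatment Groups adds that "Patients with similar injuries as the prospectively enrolled patients will be identified in this database to serve as controls", and describes the database as an "ongoing research study which collects injury characteristics, patient-reported outcomes, and kinematic/performance data for orthopaedic trauma patients with lower-extremity injuries". For opioid data on controls it says: "Our institution also has a database of all opioid prescriptions as well as risk factors". No section states how many suitable controls the database holds.

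**The concern.** TENS patients must be approached, consented, treated and followed, so a limit of 50 on that side is easy to understand. Controls are found in records, and that limit does not bind them. The protocol gives no separate argument for 50 controls, which can look like power left unused.

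The planning SD makes the question sharper. The 5.5 comes from a meta-analysis whose title in the reference list places it in total knee arthroplasty, and Background and Significance itself doubts that this literature carries over to trauma patients. If 48-hour MME varies more in this population, power falls below plan, and extra controls would be a way to buy a margin without enrolling anyone. At stake would be a real 3.5 MME difference missed for lack of precision.

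**Working it through.** **Inputs, all from Sample Size:** difference 9.9 − 6.4 = 3.5 MME; SD 5.5; two-sided 0.05; independent t-test; 40 needed and 50 enrolled. The implied loss is 1 − 40/50 = 20%; the protocol states no rate.

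**Formula.** The standard error is SE = 5.5 × √(1/n₁ + 1/n₂), and the noncentrality is 3.5/SE. Power comes from the noncentral t distribution with n₁ + n₂ − 2 degrees of freedom. Correlation within matched sets is ignored, as in the protocol's calculation.

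**Step 1: the plan's own figure.** With 40 and 40, SE = 5.5 × √(1/40 + 1/40) = 1.230 and the noncentrality is 3.5/1.230 = 2.85. Power is 80.3%. With 39 per group it is 79.2%. So 40 is the smallest number that reaches 80%, and the stated figure is correct.

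**Step 2: the plan as enrolled, and with more controls.** The protocol does not say how many TENS patients will be lost for this endpoint, so three cases are shown.

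| Evaluable TENS patients, controls kept | 1 control each | 2 controls each | 3 controls each |
|---|---|---|---|
| 40; controls of lost patients dropped (40, 80, 120) | 80.3% | 90.3% | 93.4% |
| 40; controls for all 50 kept (50, 100, 150) | 84.3% | 92.2% | 94.5% |
| 50; no loss (50, 100, 150) | 88.3% | 95.4% | 97.2% |

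The first column is the current plan. It reaches 80% in every row. The endpoint closes at 48 hours and the follow-up visits are at 2, 6 and 12 weeks, so losses at those visits need not remove the 48-hour outcome. The last row is therefore plausible, and there the gain is 7 to 9 points.

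**Step 3: protection against a larger SD.** The largest SD that keeps 80% power for 3.5 MME, with one, two or three controls each, is:
- 40 evaluable, controls for all 50 kept: 5.8, 6.6, 7.0
- no loss: 6.2, 7.2, 7.6

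If the SD were 8 (an assumption, not in the protocol), power with 40 evaluable and 50, 100 or 150 controls would be 53%, 64% and 69%. Extra controls cover a modest error in the SD and do not rescue a large one.

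**Step 4: the price.** Controls come from an earlier period. Suppose TENS has no effect but MME differs by 1.5 between periods (an assumption, not in the protocol). The chance of a significant result with one, two or three controls each is:
- 40 evaluable, controls for all 50 kept: 24.6%, 30.5%, 33.2%
- no loss: 27.2%, 34.6%, 38.3%

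In the first of these cases, three controls add 94.5 − 84.3 = 10.2 points of power and 33.2 − 24.6 = 8.6 points of false rejection. With an assumed 1.0 MME difference the rise is smaller, from 13.6% to 17.4%.

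**Step 5: what the gain would need.**
- The figure of 50 must be the number of controls. If it is the size of the database, there are no further controls to take.
- Between 50 and 100 further matches, as close as the first, must exist. The database is described as covering trauma injuries, while Inclusion Criteria admits "Operative treatment of lower extremity conditions, including fracture fixation, treatment of nonunion, and deformity correction"; extra matches for nonunion and deformity may be scarce.
- Their 48-hour inpatient MME must be obtainable. The opioid source named is a prescription database, which may not record inpatient use, so charts might have to be abstracted.

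The protocol settles none of the three.

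**The case for a change.** The best case for acting is that precision is available without enrolling anyone. The second control brings most of the gain under every loss assumption, and the proposal costs little if it fails: further controls would enter only when they match as closely as the first, and otherwise the plan stays at one each. With an assumed SD of 6.5, power for 40 evaluable patients would be 71% with 50 controls, 82% with 100 and 85% with 150. The bias of a historical comparison is present at one control each already, so extra controls do not create it.

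Much of this stands. The figures are right, the transfer of the SD from knee arthroplasty is uncertain, and a team with many close matches could well use them. It still does not make the present choice a fault. The number 50 is not unexplained: equal groups are what the calculation assumes, and 50 controls for 50 enrolled patients keeps that ratio. A protocol need not argue against every other ratio. If the SD is doubtful, the direct response is to re-examine the planning values, which is a separate matter. And although extra controls do not create bias, they make a biased comparison more likely to come out significant, so keeping one closest match per patient is a reasonable preference.

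**Conclusion.** The concern does not hold. The sample size is calculated correctly and the planned groups meet the stated 80% target at 80.3%, 84.3% or 88.3%, depending on losses. Two or three controls per patient would add 7 to 13 points of power across the three cases (95.4 − 88.3 = 7.1 at the least, 93.4 − 80.3 = 13.1 at the most). That is improvement beyond a target already met, and it depends on a supply of matches and of inpatient data that the protocol does not state. It must also be weighed against chart abstraction for up to 100 more patients, controls who may be older or lack PROMIS data, and a higher chance of a false positive if opioid use differed between periods.

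The power figures rest on the protocol's difference and SD and on its independent t-test; the false-rejection figures rest on assumed period differences. Neither set shows an error in the plan, and no change is needed.
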